Appendix 1.4. Details of Multiple Imputation Method to be Used in Sensitivity Analysis

For purposes of the missing data sensitivity analyses, the study duration of 30 months will be partitioned into 3 intervals of 10 months each. These will be referred to as period 1, period 2, and period 3, representing months 1-10, 10-20, and 20-30 respectively. Imputation models will be estimated and applied separately for each treatment group. Hospitalizations are not imputed for subjects after their death. The imputation procedure consists of two distinct phases: 1) models for cardiovascular-related hospitalization rates are estimated for each time interval, and 2) these models are then used to impute the number of cardiovascular hospitalizations following censoring (dropout) amongst subjects who dropout in an interval. Dropouts are the only source of missing hospitalization data, so there will be a monotone missing data pattern. The two-stage multiple imputation process developed here follows the procedure for monotone missing data in [Rubin \(1987\)](#).

Within each short time interval (10 months), a Poisson regression model with a constant rate will be assumed for hospitalization counts. No imputation is required for a patient who dies during the interval. Because the model applies only to subjects who survive the interval, and subjects who die during the interval are likely to have differing hospitalization rates, subjects who die in an interval will be excluded from the imputation model estimation. All other subjects still in the study at the beginning of the interval are included in the model estimation. The reduced exposure of dropouts during the intervals is represented by an exposure multiplier (between 0-10) of the monthly hospitalization rate ([McCullagh and Nelder, 1989](#)). The monthly hospitalization rate during the first period is a function of the baseline covariates NHYA baseline classification and TTR genotype. The monthly hospitalization rate during the second period is a function of the baseline covariates and the hospitalization counts during the first period. The monthly hospitalization rate during the third period is a function of the baseline covariates, and the hospitalization counts during the first and second periods.

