PROC GENMOD will be used to compute maximum likelihood estimates (MLE) of the parameters of the Poisson regression model. It will also be used to compute the variance-covariance matrix for the estimates from each time period. A total of 1000 imputed data sets will be generated. To account for estimation error when forming the imputed data sets, 1000 independent sets of the Poisson model parameters will be generated for each time period from a multivariate normal distribution with mean equal to the MLE, and with the variance-covariance matrix equal to the MLE variance-covariance matrix. The i^{th} set of Poisson model parameters from each time period are paired together, yielding 1000 sets of parameters for generating the 1000 imputed data sets. For each iteration, the individual patient Poisson rate (λ) will be generated using the Poisson regression coefficient estimates for that iteration.

The imputation process described here is applied with each set of Poisson model parameters. Subjects without complete data are comprised of two types: those with no participation during the period, and those with partial participation during the period. For those with no participation, the prediction equation will be used to impute a hospitalization count for the entire period. For those with partial participation, the prediction model will be applied to impute a hospitalization count appropriate for the remainder of the period after the patient

dropped out. The imputed value will be added to the actual observed value for that patient from the part of the period prior to their dropping out. For example, consider a patient who drops out at month 5. The patient's Period 1 imputed value will be the sum of their actual hospitalization count from month 1 to month 5 added to the predicted value from month 5 to month 10.

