Any missing data are imputed sequentially beginning with the first time period, then the second and third periods. The imputation model during the first period depends only on fully observed baseline covariates. The imputation model during the second period also depends on the hospitalization count during the first period. For any patient who dropped out during the first period, their imputed count in the first period is used in the model to produce the imputed value for that subject in period 2. Note that this differs from the process when estimating the imputation model (Rubin, 1987). A similar procedure is applied for imputation of missing values during period 3. Finally, the hospitalizations for each patient are summed to generate a complete 30-month (imputed) CV hospitalization frequency.

The null hypothesis will be tested based on the 1000 imputed data sets by computing the components of the complete-data Finkelstein-Schoenfeld statistic to yield 1000 numerator values, and 1000 denominator values (square root of the numerator variance). Following Rubin (1987), the numerators will then be averaged. The variance of this average will be the average within-imputation variance computed from the 1000 complete-data variances of the numerators combined with the between imputation variability in the numerators to yield a normal Z-statistic. The 1000 imputed hospitalization data sets will also be used to summarize hospitalization rates in the treatment groups.

Sample SAS Code

Poisson model specified below will be used to fit cardiovascular hospitalization data and will then be used to impute the missing data. The model will be fit separately for each of the 3 periods and will be done separately for both treatment groups (placebo and pooled tafamidis). Only the subjects that entered a given period (not completely missing during the period) will be used in determining the model. The "OFFSET" in the linear model implemented by PROC GENMOD is the adjustment for the exposure time in the interval (those who entered the period but did not complete the 10 months). The variable "months_exposure", used in the "OFFSET", is a log transformation of the months of exposure in a given period.

```
proc genmod data = nonmissingperiod1; ;* Only includes subjects with non-missing count data for period 1;  
class NYHAnum MUTATIONnum;  
model count = NYHAnum MUTATIONnum /dist=p link=log offset=months_exposure  
;*model terms for period1;  
output out=predpoi p=p;  
run;
```

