```

proc genmod data = nonmissingperiod2; ;* Only includes subjects with non-missing count
data for period 2;
class NYHAnum MUTATIONnum;
model count = countbase1 NYHAnum MUTATIONnum /dist=p link=log
offset=months_exposure; *model terms for period 2 where countbase1 is CV hospitalization
count from period 1;
output out=predpoi p=p;
run;

```

```

proc genmod data = nonmissingperiod3;* Only includes subjects with non-missing count
data for period 3;
class NYHAnum MUTATIONnum;
model count = countbase1 countbase2 NYHAnum MUTATIONnum /dist=p link=log
offset=months_exposure; * model terms for period 3 where countbase1 and countbase2 are
CV hospitalization counts from period 1 and 2 respectively;
output out=predpoi p=p;run;

```

The macro below can be used to perform the multiple imputation. The variable “seedval” will be the starting seed and the variable “numimp” will specify the number of multiple imputations to be performed. The dataset “withmissing” will contain all the subjects that will be imputed.

```

%macro impute (output, seedval, numimp);
data &output;
set withmissing;
seed=&seedval;
do MInum = 1 to &numimp;
lambda= exp( $\pm$  x.xx  $\pm$  x.xxx countbase(varies depending on the period)  $\pm$  x.xx *NYHAnum
 $\pm$  x.xx*MUTATIONnum);
count = ranpoi(seed, lambda); * coefficients will be randomly generated from a normal
distribution based on the estimates and standard error output from PROC GENMOD;
output;
end;
run;
%mend impute;

```

The macro input statement will use a seed value of 999 and perform 1000 multiple imputations.

```

%impute (impute2, 999, 1000);

```

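### SAP Appendix 1.4: the sample imputation macro omits the months-missing factor its own text requires; coded as printed, a wholly missed 10-month period is imputed at one tenth of the intended mean

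*SAP*

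**What the plan says.** SAP Appendix 1.4 splits the 30 months into three 10-month periods and fits a Poisson model in each, separately by treatment group.

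- **Rate and exposure.** A dropout's reduced exposure is "represented by an exposure multiplier (between 0-10) of the monthly hospitalization rate". The GENMOD fits use a log link with the offset `months_exposure`, which "is a log transformation of the months of exposure in a given period".
- **What is imputed.** A subject absent for a whole period gets a count for all of it. For a subject who took part in some of the period, "the prediction model will be applied to impute a hospitalization count appropriate for the remainder of the period after the patient" left. Then: "The imputed value will be added to the actual observed value for that patient".
- **Carry-forward.** For a first-period dropout, "their imputed count in the first period is used in the model to produce the imputed value for that subject in period 2".
- **Parameter uncertainty.** The text states that "1000 independent sets of the Poisson model parameters will be generated for each time period from a multivariate normal distribution", using the full variance-covariance matrix of the estimates.
- **Use of the result.** Besides the combined Finkelstein-Schoenfeld statistic, "The 1000 imputed hospitalization data sets will also be used to summarize hospitalization rates in the treatment groups".

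The sample macro sets lambda to the exponential of an intercept, the prior-period count, NYHA and mutation terms. It then draws: "count = ranpoi(seed, lambda); * coefficients will be randomly generated from a normal". The rest of that comment bases the normal draws on the estimates and standard errors from GENMOD.

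**The concern.** With an offset of log(months), the exponential of the linear predictor without the offset is a rate for one month. The macro uses that one-month rate as the mean for whatever stretch is missing, up to 10 months. No exposure, offset or months-missing variable appears in it, and the later steps only sum the period counts.

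Two smaller mismatches sit beside this. The macro does not add the observed part-period count, and its comment mentions standard errors only, which would lose the covariances that the text requires.

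This is the multiple-imputation check on missing hospitalization data in the primary analysis. Coded as printed, surviving dropouts would look almost free of admissions after leaving, and the summarized rates would be too low in both arms. The error would be hard to notice, because the macro would still return plausible small integers.

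**Working it through.** The SAP states no imputed mean, so there is no figure of its own to reproduce.

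**Inputs**
- Period length 10 months, offset log(months): SAP Appendix 1.4.
- Planning counts 2.5 (placebo) and 1.5 (tafamidis): Protocol Section 9.1. That section gives no time unit for the counts. Reading them as 30-month totals is an assumption, used only to show size. Monthly rates: 2.5/30 = 0.0833 and 1.5/30 = 0.05.

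**Ratio for one period.** The fitted model is log E(count) = Xb + log(months).
- Intended mean = months missing × exp(Xb); macro mean = exp(Xb).
- Ratio = 1/(months missing): 1/10 for a whole period, 1/5 for Period 1 in the SAP's own Month 5 example, and 2 if half a month is missing.
- Whole period, intended v macro: placebo 0.833 v 0.083, tafamidis 0.50 v 0.05.
- Check by simulation (Poisson fit with log-months offset, 200,000 subjects per arm): the macro draw was 0.0996 (placebo) and 0.0991 (tafamidis) times the mean count in complete periods; multiplying lambda by 10 gave 1.00 in both arms.
- An offset in fractions of a period would have made the macro correct, but the SAP states months.

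**Through Month 30, placebo rate r = 0.0833.** For dropout at month d, with k the number of periods wholly or partly missing: required = r(30 − d), macro = rk, ratio = k/(30 − d). This takes a constant rate and ignores any effect of the prior-period count.

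| Dropout month | Required | Macro | Ratio |
|---|---|---|---|
| 5 | 2.08 | 0.25 | 12% |
| 10 | 1.67 | 0.17 | 10% |
| 15 | 1.25 | 0.17 | 13% |
| 20 | 0.83 | 0.08 | 10% |
| 25 | 0.42 | 0.08 | 20% |
| 28 | 0.17 | 0.08 | 50% |
| 29 | 0.08 | 0.08 | 100% |
| 29.5 | 0.04 | 0.08 | 200% |

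For a Month 10 dropout the planned placebo-minus-tafamidis difference in imputed admissions is (0.0833 − 0.05) × 20 = 0.67 as required, and (0.0833 − 0.05) × 2 = 0.07 from the macro.

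**Carry-forward.** Where Period 1 was also imputed, its low count enters the Period 2 model. With assumed prior-count coefficients of 0.1 to 0.5 at the placebo rate, and both periods wholly missed, the Period 2 ratio falls from 0.10 to between 0.091 and 0.062.

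**Summarized rates (illustration).** Assume that surviving dropouts leave evenly over 30 months, that the rate is constant, and that the programmer does add the observed count. Dropout shares are not in the documents.
- Mean required 15r, mean macro (3 + 2 + 1)/3 × r = 2r, shortfall 13r out of 30r.
- Mean over surviving subjects = R × (1 − (13/30) × p), for planning count R and dropout share p.
- Placebo at p = 10%, 20%, 30%: 2.39, 2.28, 2.18 instead of 2.50.
- Rate ratio = 0.60 × (1 − 0.433 p_taf)/(1 − 0.433 p_pbo): 0.60 with equal dropout, 0.63 at 20% placebo/10% tafamidis, 0.57 at 10%/20%.
- Check by simulation of 400,000 placebo dropouts: mean 30-month count 2.50 with the exposure term and 1.41 with the macro (formula 17r = 1.42).

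**The case against.** The strongest reply is that the specification is right and the code only illustrates it. The text gives the exposure multiplier, the whole-period and remainder rules and a worked Month 5 example. The macro cannot run as printed: its coefficients are x.xx placeholders and it is introduced as code that can be used, so someone must rewrite the line. It also omits the carry-forward, the 30-month sum and the test itself, so leaving out the observed count may only mean that it illustrates the draw. The comment on standard errors may be shorthand for the joint draw set out in the text.

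The effect on the test also looks modest. An unstratified Finkelstein-Schoenfeld simulation was run with 160 v 240 subjects, mortality 25% v 17.5%, plain Poisson counts of 2.5 v 1.5, evenly spread dropout among survivors, known rates, the observed count added and no carry-forward. Mean z, correct v macro, was:

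- equal dropout of 10%, 20%, 30%: 5.25 v 5.10, 5.15 v 4.88, 5.13 v 4.69;
- 20% placebo/10% tafamidis: 5.20 v 4.63;
- 10% placebo/20% tafamidis: 5.18 v 5.31.

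That is a loss of about 3% to 11% of z, or a small gain in the last case. Plain Poisson counts are optimistic, so these values are illustrative only.

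Most of this stands as a limit on weight. It does not remove the contradiction. Placeholder coefficients cannot supply the missing factor: they come from the GENMOD output and so are monthly, and no single constant fits partly missed periods whose length varies by subject. The sponsor has also treated sample-code errors as worth amending. SAP Section 1 records an added RANDOM statement, a corrected ESTIMATE statement, and detail added to the Appendix 1.4 code for clarity.

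**Conclusion.** The concern holds: the macro contradicts the text of its own appendix and should be corrected. Given the covariates and prior-period counts, the factor of 1/10 for a wholly missed period, and 1/(months missing) for a partly missed one, is exact and needs no assumption. The macro under-imputes when more than one month of a period is missing and over-imputes when less than one month is missing.

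Harm arises only if the lambda line is carried into the program, and then only in pairs of subjects not already decided by mortality. The direction of any between-arm bias depends on differential dropout, which the documents do not give. The primary test (no imputation, SAP Section 7), the key secondary endpoints and control of alpha are unaffected. It should be fixed, but it does not threaten the trial's main conclusion. The observed-count and comment mismatches are secondary and can be corrected in the same edit.

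**What to change.** Before unblinding, bring the Appendix 1.4 macro into line with its text:

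1. Set lambda = months_missing × exp(linear predictor), with months_missing equal to 10 for a wholly missed period and 10 minus the months observed in that period otherwise.
2. Set the period count to the observed part-period count plus the draw, and pass that total into `countbase1` and `countbase2` for later periods.
3. Reword the comment so that coefficients are drawn jointly from a multivariate normal with the GENMOD variance-covariance matrix.

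The cost is a few lines of sample code and one comment. Data, design and the primary analysis do not change.

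### In SAP Appendix 1.4 the sample macro's comment builds the imputation coefficients from standard errors alone, while the text requires a joint draw from the full covariance matrix

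*SAP*

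**What the plan says.** The multiple-imputation analysis is a sensitivity check on the primary Finkelstein-Schoenfeld test (SAP Sections 7 and 8.2.4). Its method is in SAP Appendix 1.4.

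- **Text.** A Poisson model is fitted in each of three 10-month periods: "Imputation models will be estimated and applied separately for each treatment group". Of GENMOD it says: "It will also be used to compute the variance-covariance matrix for the estimates from each time period". For each period, 1000 parameter sets are drawn "from a multivariate normal distribution with mean equal to the MLE" and "with the variance-covariance matrix equal to the MLE variance-covariance matrix". The i-th sets from the three periods together generate the i-th imputed data set, so all subjects in an arm share the same coefficients within an imputation.
- **Sample code.** The period 1 call is "model count = NYHAnum MUTATIONnum /dist=p link=log offset=months_exposure"; periods 2 and 3 add the earlier counts. Each of the three calls saves only predicted values. The macro is introduced with "The macro below can be used to perform the multiple imputation". Its coefficients are printed as x.xx placeholders, and its only random call is the Poisson draw of the count. A comment beside that call, inside the per-subject data step, says the coefficients will be generated from a normal "distribution based on the estimates and standard error output from PROC GENMOD".

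**The concern.** Standard errors carry no covariances, so the inputs named in the comment cannot produce the joint draw that the text requires. The intercept is negatively correlated with the NYHA and genotype effects. Drawing each coefficient from its own standard error discards that correlation and makes the linear predictor too variable in every cell except the reference cell.

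The excess enters the result in two ways. Appendix 1.4 adds between-imputation variance to the within-imputation variance to form the Z statistic, so a shared but over-dispersed draw lowers Z. The rates are also exponentiated, so extra variance on the log scale raises the mean imputed rate, and the imputed data sets are used to summarise hospitalization rates by arm. Two programmers working from the same appendix could report different sensitivity results.

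**Working it through.** The documents give no figure for this effect, so there is none to reproduce.

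**Inputs from the documents.** Arms of 160 placebo and 240 pooled tafamidis subjects (SAP Section 2.1). Planning means of 2.5 and 1.5 cardiovascular hospitalizations (Protocol Section 9.1), read as totals over 30 months, which gives 0.833 and 0.5 per period. At least 30% of each genotype (SAP Section 2.1).

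**Assumptions.** NYHA III share 20% to 50%; variant share 30% to 70%; factors independent; equal rates in all cells; 0/1 dummy coding; either level of each factor as reference.

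**Period 1 formula.** Let p and q be the shares in the non-reference NYHA and genotype levels, and M the expected events in the arm. Multiplied by M, the variances are:

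- intercept: 1 + p/(1−p) + q/(1−q)
- NYHA effect: 1/[p(1−p)]
- genotype effect: 1/[q(1−q)]

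The log-rate variance averaged over subjects is 3/M under the joint draw (three parameters). Under separate draws it is [1 + (1+p)/(1−p) + (1+q)/(1−q)]/M. M cancels in the ratio, which is therefore the same in both arms.

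| p | q | Separate × M | Ratio to 3 |
|---|---|---|---|
| 0.2 | 0.3 | 4.36 | 1.45 |
| 0.3 | 0.3 | 4.71 | 1.57 |
| 0.5 | 0.5 | 7.00 | 2.33 |
| 0.7 | 0.7 | 12.33 | 4.11 |
| 0.8 | 0.7 | 15.67 | 5.22 |

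Over the whole grid the ratio runs from 1.45 to 5.22, with median 2.56. For periods 2 and 3, with earlier counts as covariates, it is about 1.5 to 4.6.

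**By cell.** In the reference cell the ratio is 1. In the doubly non-reference cell with p = 0.8 and q = 0.7, separate draws give 1 + 4 + 2.333 + 6.25 + 4.762 = 18.35 and the joint draw gives 1 + 0.25 + 0.429 = 1.679. The ratio is 10.9, the largest found.

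**Imputed rates.** The upward shift is about exp[(separate − joint variance)/2] − 1. For tafamidis in period 1, M = 240 × 0.5 = 120, ignoring death and dropout.

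- p = q = 0.5: exp[(7 − 3)/240] − 1 = 1.7%
- p = 0.2, q = 0.3: exp[(4.36 − 3)/240] − 1 = 0.6%
- p = 0.8, q = 0.7: exp[(15.67 − 3)/240] − 1 = 5.4%

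Simulating the imputation gave about 2% to 3%, whether coefficients were shared or redrawn per subject. Each arm has its own model, so both would shift upward.

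**Effect on Z.** The three-period imputation with Finkelstein-Schoenfeld pooling was simulated at N = 400 with a 30% mortality reduction. B and W are the between- and within-imputation variances of the numerator. With 1000 imputations, Z changes by the factor √[(1 + B/W joint)/(1 + B/W separate)].

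| Assumed dropout | B/W joint | B/W separate | Total variance ratio | Mean Z joint | Mean Z separate |
|---|---|---|---|---|---|
| 10% | 0.025 | 0.030 | 1.030/1.025 = 1.005 | 4.71 | 4.69 |
| 25% | 0.064 | 0.094 | 1.094/1.064 = 1.03 | 4.78 | 4.71 |
| 40% | 0.138 | 0.229 | 1.229/1.138 = 1.08 | 4.38 | 4.22 |

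B itself rises 1.20-, 1.45- and 1.64-fold, and Z falls by 0.02, 0.07 and 0.16.

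These losses depend on the reference levels. I repeated the simulation with 30% NYHA III, 40% variant, no extra-Poisson variation and 50 simulated trials per setting. With NYHA I/II and wild-type as reference the losses were 0.01, 0.06 and 0.18. With NYHA III and variant as reference they were 0.04, 0.23 and 0.59, and the upward shift in rates was 6% to 8%. The range 0.02 to 0.16 is therefore not a ceiling.

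**Redrawing for each subject.** The comment sits inside the subject loop. If coefficients were redrawn there, parameter error would no longer be shared across subjects. Simulated B was then about 0.8 to 0.96 of its joint-draw value, with the gap narrowing at low dropout.

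**The case against.** The best defence is that the method is already stated correctly. The text specifies the joint draw, says GENMOD will supply the covariance matrix, and pairs one parameter set per period with each imputation. The code is labelled as a sample and is schematic: it contains no coefficient draw, and its GENMOD calls do not save the estimates or standard errors either. The comment never says that coefficients are drawn one at a time, and the production program is not in the documents. All of this stands.

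A reader might therefore infer too much in three ways:

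- **That the macro draws each coefficient separately.** The code does not. Separate drawing is the natural reading of a loose comment, not a coded step.
- **That one inflation factor applies, such as 3.5-fold.** That value lies inside the range, but the documents give no NYHA III share, only a floor for genotype, and no reference level or coefficient covariances.
- **That the sensitivity analysis will be wrong, always toward a smaller Z.** That requires the program to follow the comment over the text and also to share one draw within each imputation. A per-subject redraw moves the between-imputation variance the other way.

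What the defence does not remove is the contradiction. The comment is the only instruction in the code on how coefficients are generated, and the SAP does not say which statement prevails.

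**Conclusion.** The point holds as an inconsistency within Appendix 1.4, and it is minor. If the comment were followed with independent draws shared within an imputation, the parameter variance of imputed log-rates would be overstated about 1.5- to 5-fold on average and 1- to 11-fold by cell. Imputed rates would be slightly too high. The sensitivity Z would be too low by about 0.02 to 0.16 at 10% to 40% dropout in the main simulation, and by more if the less common levels were the reference and dropout were high. That error is conservative. With a per-subject redraw the between-imputation variance would be understated instead.

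The sizes rest on assumed NYHA and genotype shares, dummy coding, the planning rates and assumed dropout; none is an estimate for this trial. SAP Section 7 rules out imputation in the primary analysis, so its result does not depend on this point.

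**What to change.** In SAP Appendix 1.4:

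1. Add the covariance-matrix output (COVB) to the GENMOD fit for each period and arm, and save it with the estimates.
2. Draw one coefficient vector jointly from the multivariate normal for each imputation, period and arm, outside the subject loop, and merge it to subjects by imputation number.
3. Reword the macro comment to describe that draw.

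This brings the sample code into line with the method already in the text. It costs a few lines of code and changes nothing in trial conduct, data collection or the primary analysis.
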